2.3 Sample Size Determination

Approximately 150 participants will be screened in this study to assure approximately 100 participants are assigned to the open-label treatment with mirdametinib. These 100 participants will be stratified by age, with 50 participants ages 2 to 17 years for the pediatric cohort and 50 participants ≥ 18 years of age for the adult cohort. The sample size was calculated separately for each stratum to allow for different hypothesized magnitudes of response depending on the age group of the participants.

An observed objective response rate (ORR) of at least 42% (at least 21 objective responses) in 50 treated adult participants will result in a lower bound of the 95% confidence interval (CI) that excludes 28%. This will be considered evidence of clinically significant activity of mirdametinib. This is equivalent to testing a null ORR rate of 23% compared to a target rate of 43% with 80% power and 2-sided alpha of 0.05. Similarly, an observed ORR of 64% (at least 32 objective responses) in 50 treated pediatric participants will result in a lower bound of the 95% CI that excludes 49%.

For the analysis of safety, there is a 95% chance of observing at least 1 adverse event (AE) that occurs at an underlying rate of 3.0-% in a sample size of 100 participants.

The assumptions for the response rate in the adult population used for the basis of sample size estimation are based on the study conducted by Weiss et al (Weiss 2017). As outlined in Section 2.1, the preliminary results from this study describe an ORR (as defined by a 20% reduction by of the target lesion from baseline) of 42% (95% Cl: 20% to 67%) in response to one year of mirdametinib therapy. The results of tumor response post-therapy at > 1 year have not yet been released. This finding is consistent with the preliminary data of cabozantinib in patients with a morbid or progressing PN. In a Phase 2 study of cabozantinib in adults > 16 years of age with an evaluable PN, 8 of 19 patients achieved an objective response (42%) (Shih, 2018).

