4.1.1 Primary Efficacy Measure

The primary efficacy endpoint of interest is the confirmed ORR by the end of Treatment Phase (i.e., Cycle 24). The confirmed ORR is defined as the proportion of participants who have a confirmed ≥ 20% reduction in target tumor volume as compared to baseline as assessed by a BICR, and the response needs to be confirmed by BICR in a consecutive tumor assessment within 2 − 6 months.

To determine the level of target tumor response (complete response [CR], partial response [PR], stable disease [SD], or progressive disease [PD]) which are described below, post-baseline measurement scans are compared to the target PN volume in the pre-treatment MRI scan using volumetric data analysis:

- CR: A complete resolution of the target PN
- PR: A ≥ 20% reduction in the volume of the target PN lesion compared to baseline
- SD: Between a < 20% increase and < 20% decrease in the volume of the target PN lesion compared to baseline
- PD: A ≥ 20% increase in the volume of the target PN compared to baseline. (Radiographic disease progression)

The best overall confirmed response (CR, PR, SD, PD, NE - where SD/PD/NE only require a singular response to be deemed confirmed at that level) will be summarized. For participants that remain on treatment after PD, only the best response up to PD will be considered. For participants who only have one response measurement, and this is a CR or PR (and therefore unconfirmed), their best overall response status will be set to "Missing".

All tumor volume measurements will be independently calculated by two BICR readers. In the case that the two measurements represent different tumor response statuses, as defined above, an independent adjudicator will make the final decision on which response category is recorded at that visit. The primary endpoint analysis will be performed using the adjudicator-selected reader for those visits where the two BICR readers did not agree.

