Document: S:\Q_146\Q_03974\MEK-NF-201\Prog_Stat\Documentation\SAP\MEK-NF-201 SAP v1.0.0.docx
Author:

Statistical Analysis Plan SpringWorks Therapeutics Protocol Number: MEK-NF-201

In addition to the anchor-based estimates described above, the number and percentage of participants with a within-patient meaningful score change estimates are defined below and will be considered as a supportive analysis. For PedsQL Scale Scores, the meaningful score difference will be defined separately for adult, pediatric self-report, and pediatric parent proxy data. In each case, it will be defined as 0.5*SD, where SD is calculated from the baseline Scale Score data. This is in-line with the difference used on the selumetinib SPRINT study (Gross, 2018) and serves as the lower bound for minimally detectable change (Norman, 2003).

The number and percentage of participants with a change representing a clinically meaningful improvement (alongside associated 95% Clopper-Pearson Cls) will be presented for both thresholds.

In addition, within each age cohort, the proportion of participants reaching the anchor-based and distribution threshold will be analyzed in the subgroup of participants who have a confirmed objective response status versus the subgroup of those who do not. This is to further characterize the relationship between PRO improvement and the clinical endpoint of tumor response. The proportion of participants reaching the anchor-based (and distribution) thresholds will be summarized with 95% Clopper-Pearson Cls by confirmed objective response status, and the differences in the proportions of participants reaching the anchor-based/distribution thresholds between responders and non-responders will be tested using a Chi-Square test at a 5% significance level.

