6.11.2.3 Change from Baseline in pain (assessed using the NRS-11 and PII)

6.11.2.3.1 NRS-11

All NRS-11 records will be listed by participant and visit.

The number and percentage of participants in each of the result categories (Appendix 1.3) at baseline will be summarized. Absolute values and change from baseline will be summarized overall and by confirmed objective response status (as defined with confirmed response rate in Section 4.1.1 using adjudicated values where appropriate), by visit and age cohort, the summaries presented will be number and percentage of participants with a non-missing score, mean, SD, median, minimum, and maximum values.

For NRS-11, a within-patient meaningful score change, or meaningful score difference (FDA, 2023), will be derived by anchor-based analysis of the study's data as described in the meaningful change threshold analysis plan (Version 1.0, dated 12Sep2023). The primary focus of this will be on if such a relevant difference exists at Cycle 13.

Additionally the number and percentage of participants with a change representing a clinically meaningful improvement (alongside associated Clopper-Pearson confidence intervals) will be presented using change from baseline of ≤ -1 (This cut point has previously been researched and assessed as a meaningful change in pediatric populations (Hirschfeld, 2014)), representing a clinically meaningful improvement, will be presented, as well as change from baseline greater than the within-patient meaningful change threshold (i.e., derived by anchor-based analysis of the study's data in accordance with the MCT SAP; see Section 5.8 above) will be presented.

In addition, within each age cohort, the proportion of participants reaching the anchor-based and distribution threshold will be analyzed in the subgroup of participants who have a confirmed objective response status versus the subgroup of those who do not. This is to further characterize the relationship between PRO improvement and the clinical endpoint of tumor response. The proportion of participants reaching the anchor-based (and distribution) thresholds will be summarized with 95% Clopper-Pearson Cls by confirmed objective response status, and the differences in the proportions of participants reaching the anchor-based/distribution thresholds between responders and non-responders will be tested using a Chi-Square test at a 5% significance level.

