6.11.3.6 Change in Tumor Volume

Target tumor volume, change from baseline in tumor volume, and percentage change from baseline in tumor volume calculated as per Section 5.1.2 will be summarized by the number of participants, mean, SD, median, minimum, and maximum values by visit for each age cohort separately. This will be presented by averaging the volume across the two readers (unless response adjudication was performed) and reported separately for each reader (A vs B) from the BICR data, since the volumetric measurement was not triggered for adjudication.

An MMRM will be fit separately by age cohort with change from baseline in tumor volume as the dependent variable, visit as a fixed effect and baseline tumor volume as a covariate. The covariance structure will be decided in the manner described in Section 6.11.2.2, and a Kenward-Roger approximation will be used for the degrees of freedom. This model will be fitted for each cohort for all scheduled visits up until the first point where there are fewer than 5 participants with valid tumor volume measurements. EOT visits will be mapped to the closest scheduled tumor visit following the rules outlined in Table 12 and will only be included in the model if the participant has no other record at that timepoint. LS Means estimates will be presented with associated standard errors, 95% Cls and p-values by visit. Plots of the LS Means estimates over time with associated 95% Cl bands will be presented separately by age cohort.

Best volumetric percentage change from baseline as well as the time, in months, to the best volumetric percentage change from baseline will be summarized by the number of participants, mean, SD, median, minimum, and maximum. This will be presented by averaging the volume across the two readers (unless response adjudication was performed) and reported separately for each reader (A vs B) from the BICR data. In addition, a waterfall plot of the best volumetric % change from baseline will be presented using the average (unless adjudication of response occurred), and by the two readers separately.

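### The SAP's only formal test linking PRO improvement to tumor response cuts PRO change at a threshold, which costs roughly 7 to 28 points of power under two assumed models

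*SAP*

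**What the plan says.** SAP 6.11.2.2 gives the purpose of the comparison: "This is to further characterize the relationship between PRO improvement and the clinical endpoint of tumor response". Within each age cohort, the proportions reaching the anchor-based and the distribution-based threshold are set out by confirmed response status, and the difference "between responders and non-responders will be tested using a Chi-Square test at a 5% significance level". Sections 6.11.2.3.1 (NRS-11) and 6.11.2.3.2 (PII) repeat this.

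The cuts are as follows.
- **PedsQL, distribution threshold:** "In each case, it will be defined as 0.5*SD, where SD is calculated from the baseline Scale Score data".
- **NRS-11, fixed cut:** "presented using change from baseline of ≤ -1".
- **PII, distribution threshold:** half a baseline SD.
- **All three:** an additional anchor-based threshold, to be derived from the trial's own data.
- **Response:** the primary endpoint, the "proportion of participants who have a confirmed ≥ 20% reduction in target tumor volume as compared to baseline as assessed by a BICR", with confirmation on a further scan (SAP 4.1.1).

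The full-scale PRO change is analysed by MMRM, but SAP 5.3 allows baseline score as the only covariate and response status is not a factor. Full-scale change by response status appears as summary statistics and plots, without a test.

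**The concern.** PRO change is measured on a fine scale: PedsQL runs from 0 to 100, and NRS-11 and PII are averaged over up to seven days. Cutting it into reached or not reached treats a change just above the threshold like a very large one, and a change just below it like a deterioration. In groups of about 21 and 29, that loss of information matters.

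Two features make it worse.
- **No baseline adjustment.** The SAP's own MMRMs adjust for baseline score. On NRS-11, a participant whose baseline pain is below 1 cannot fall by 1 point, so can only count as not improved. Protocol inclusion criterion 3 admits tumors for morbidity other than pain, so such participants are possible.
- **Fewer children.** NRS-11 is completed from age 8 and PII from age 6, so the pediatric tables for these scores will hold fewer than the full cohort.

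At stake is how a non-significant result would be read. A test with low power can miss a moderate association between symptom benefit and response.

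**Working it through.** **1. The plan's own figures.** The SAP states no power, effect size or correlation for this test. Its figures for n = 50 concern ORR, and they reproduce. The exact lower 95% bound is 28.2% for 21/50 and 49.2% for 32/50. An exact test of 23% against 43% has 80.4% power. Nothing below contradicts a stated number.

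**2. Inputs.**
- Cohort size, from SAP 2.3: "with 50 participants ages 2 to 17 years for the pediatric cohort and 50 participants ≥ 18 years of age for the adult cohort" (approximately 50 each elsewhere). n = 30 stands for a reduced pediatric subset and is an assumption.
- Responder share: 42% and 64% from SAP 2.3 (for adults, "An observed objective response rate (ORR) of at least 42% (at least 21 objective responses) in 50 treated adult participants"), and 44% from SAP 7.1.
- Share reaching the PRO threshold: 30% or 40%. Assumed.
- Link between PRO change and tumor change: bivariate normal with correlation ρ = 0.3 to 0.5, or a mean shift of 0.5 to 0.9 SD between responders and non-responders. Assumed.

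**3. Worked case: n = 50, 42% responders (21 against 29), 40% improvers, ρ = 0.4.** Response is kept binary in both analyses.

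*Chi-square.* The model gives improver proportions p₁ = 0.549 in responders and p₀ = 0.292 in non-responders (check: 0.42 × 0.549 + 0.58 × 0.292 = 0.400).
- Null SE = √[0.40 × 0.60 × (1/21 + 1/29)] = 0.140.
- Alternative SE = √[0.549 × 0.451/21 + 0.292 × 0.708/29] = 0.138.
- Power = Φ[(0.257 − 1.96 × 0.140)/0.138] ≈ **45%**.

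*Comparison of mean PRO change.*
- Mean difference = ρ·φ(z)/[p(1 − p)] = 0.4 × 0.391/(0.42 × 0.58) = 0.642 SD.
- Within-group SD = √[1 − 0.42 × 0.58 × 0.642²] = 0.948, so the standardized difference is 0.642/0.948 = 0.677.
- Noncentrality = 0.677 × √(21 × 29/50) = 2.36, and a t-test on 48 df has power of about **64%**.

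The difference is about 19 points. Simulation agrees (chi-square 41 to 45%, t-test 63%).

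**4. Range, by simulation, two-sided 5%.**

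| Model | n | Chi-square | t-test of PRO change |
|---|---|---|---|
| Bivariate normal, ρ = 0.4 | 50 | 36–47% | 61–64% |
| Bivariate normal, ρ = 0.4 | 30 | 22–30% | 39–42% |

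Over n = 30 to 50 and both the bivariate-normal and mean-shift models, the gain from keeping PRO change on its full scale is about 7 to 28 points. It is smallest at n = 30 with ρ = 0.3, and largest at n = 50 with ρ = 0.5 and a 64%/30% split. The t-test has no baseline covariate, so any further gain from ANCOVA is not counted. Type I error is close to 5% for both tests.

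**5. A model that favors the cut.** Suppose 55% of responders and 20% of non-responders get a large benefit and the rest get none. In one version of this model the chi-square has 43 to 69% power and the t-test 38 to 63%, a loss of about 5 points. In another version the t-test gains 1 to 3 points.

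**6. Expected cell counts.** The smallest expected count is n × (smaller response share) × (improver share). At n = 30:
- 42%/40%: 30 × 0.42 × 0.40 = 5.04
- 64%/40%: 30 × 0.36 × 0.40 = 4.32
- 42%/30%: 30 × 0.42 × 0.30 = 3.78
- 64%/30%: 30 × 0.36 × 0.30 = 3.24

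Around these averages, the smallest expected count is below 5 in about 54 to 95% of simulated tables. At n = 50 the share is at most about 42%. The SAP names no exact alternative.

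**The case against.** The strongest defense is that the test links two prespecified endpoints. Confirmed response is the primary endpoint, and SAP Table 1 lists the number of participants with a meaningful score change as a secondary endpoint for quality of life and for pain. The analysis is described as further characterization, with no power claim and no decision rule attached. Mean and SD of PRO change by response status are already tabulated, so an unadjusted mean difference can be derived from planned output. All of this stands. It is the reason to keep the threshold proportions, and it limits the weight of the point.

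The power figures also rest on assumed models. Protocol 4.2 itself notes symptom improvement without a matching fall in tumor size, so the documents support no particular correlation. That stands too, and step 5 shows a case where the cut loses nothing.

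A reader might go further and infer that the tumor measure should also be kept continuous, since SAP 6.11.3.6 already derives "percentage change from baseline in tumor volume". On that reading the loss would be put at about 15 to 37 points, and a correlation with volume change would replace the test. The documents do not support this. The stated question concerns tumor response, which is binary by definition and is confirmed at any time up to Cycle 24. Volume change at Cycle 13 is a different question, and it drops anyone without a scan at that visit. The larger figure also depends on a linear bivariate-normal link. If benefit follows response status, the correlation gains roughly −1 to +3 points over the chi-square. If a subset benefits, it loses 5 to 7 points in one version of the model and 19 to 27 in another.

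**Conclusion.** The concern holds for the PRO cut. Within this SAP the sole formal test of the PRO-response link is an unadjusted chi-square on thresholded PRO change. With response kept binary, the cut costs roughly 7 to 28 points of power at n = 30 to 50 under the bivariate-normal and mean-shift models. If only a subset of participants benefits, the effect ranges from a gain of 1 to 3 points to a loss of about 5. The correlation, the distribution and the improver share are all assumptions.

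The sparse-table point is a gap in specification. Simulated type I error stays near 5%, so no inflation has been shown.

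A reader might also infer that a null result would undermine the volumetric endpoint, or that the plan fails a power target. The SAP gives this test neither role. The analysis is supportive, and the change is worth making because it is cheap and answers the same question with more information.

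**What to change.** In SAP 6.11.2.2, 6.11.2.3.1 and 6.11.2.3.2:
- Make the 5% test an ANCOVA of PRO change from baseline at Cycle 13 (the visit fixed in SAP 5.8) on confirmed response status, with baseline PRO score as covariate. Fit it by cohort and questionnaire type, and report the adjusted mean difference with its 95% CI.
- Keep the proportions reaching the anchor-based and distribution thresholds by response status, with Clopper-Pearson intervals. If they are still tested, specify an exact test when expected counts fall below 5.
- A correlation of PRO change with percentage volume change at Cycle 13 may be added as exploratory. It should not replace the comparison by response status.

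The cost is SAP wording and a few model outputs from data already collected. The main result becomes a mean difference instead of a difference in proportions, which stays in the table.

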An MMRM will be fitted separately by age cohort and questionnaire type for each PedsQL score listed in Section 4.1.2.2.1. Change from baseline in PedsQL score will be the dependent variable, visit will be fitted as a fixed effect, and baseline PedsQL score used as a covariate. Covariance structures will be trialed in the order of decreasing complexity, with the first structure that converges without error used. The structures tested are as follows: Unstructured, Heterogenous Toeplitz, Heterogenous Autoregressive, Autoregressive, Heterogenous Compound Symmetry, Compound Symmetry, Variance Components. A Kenward-Roger approximation will be used for the degrees of freedom. This model will be fitted twice, once using only data through Cycle 13, and once including data from the entire study (timepoints with < 5 subjects will not be presented). EOT and unscheduled visits will be mapped to the closest scheduled tumor visit following the rules outlined in Table 13, and will only be included in the model if the participant has no other record at that timepoint. For the MMRM change from baseline tables, the least square (LS) Means estimates will be presented with associated standard errors, 95% Cls and p-values by visit. Plots of the LS Means estimates over time with associated 95% Cl bands will be presented separately by age cohort and questionnaire type for both models.

Box and whiskers plots of change from baseline in total score will be presented by visit and confirmed objective response status for the adult cohort, pediatric cohort self-report, and pediatric cohort parent proxy separately.

A waterfall plot of change from baseline will be presented by visit for adult cohort, pediatric cohort self-report and pediatric cohort parent proxy separately for each PedsQL domain at Cycles 5 and 13 with a line representing the respective within-patient meaningful change threshold derived by anchor-based analysis. This plot will be color-coded by confirmed objective response status.

Additionally, a sensitivity analysis will be performed for each PedsQL score using the imputed data described in Section 5.5.1.1. The MMRM analysis described above will be performed with data up to Cycle 13. LS Means estimates, associated standard errors, 95% Cls and p-values will be presented by visit.

Document: S:\Q_146\Q_03974\MEK-NF-201\Prog_Stat\Documentation\SAP\MEK-NF-201 SAP v1.0.0.docx

Author:

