An MMRM will be fit separately by age cohort with change from baseline in NRS-11 score as the dependent variable, visit as a fixed effect and baseline NRS-11 score as a covariate. The covariance structure will be decided in the manner described in Section 6.11.2.2, and a Kenward-Roger approximation will be used for the degrees of freedom. This model will be fitted twice, once using only data through Cycle 13, and once through Cycle 24. EOT visits will be mapped to the closest scheduled tumor visit following the rules outlined in Table 13, and will only be included in the model if the participant has no other record at that timepoint. LS Means estimates will be presented with associated standard errors, 95% Cls and p-values by visit. Plots of the LS Means estimates over time with associated 95% Cl bands will be presented separately by age cohort for both models.

Box and whiskers plots of change from baseline will be presented by visit and confirmed objective response status for each age cohort separately.

A waterfall plot of change from baseline in NRS-11 will be presented by visit for adult cohort, pediatric cohort self-report and pediatric cohort parent proxy separately at Cycles 5 and 13, with a line representing the respective within-patient meaningful change threshold derived by anchorbased analysis. This plot will be color-coded by confirmed objective response status.

Document: S:\Q_146\Q_03974\MEK-NF-201\Prog_Stat\Documentation\SAP\MEK-NF-201 SAP v1.0.0.docx
Author:

Additionally, a sensitivity analysis will be performed on the NRS-11 results using the imputed data described in Section 5.5.1.2. The MMRM analysis described above will be performed with data up to Cycle 13. LS Means estimates, associated standard errors, 95% Cls and p-values will be presented by visit.

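### The fallback list of covariance structures for the repeated-measures models breaks its own rule of decreasing complexity by placing Autoregressive before Heterogenous Compound Symmetry

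*SAP*

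**What the plan says.** SAP 6.11.2.2 (PedsQL) describes a mixed model for repeated measures and gives the selection rule for its covariance matrix: "Covariance structures will be trialed in the order of decreasing complexity, with the first structure that converges without error used". The order is then written out: "Unstructured, Heterogenous Toeplitz, Heterogenous Autoregressive, Autoregressive, Heterogenous Compound Symmetry, Compound Symmetry, Variance Components". On inference it adds: "A Kenward-Roger approximation will be used for the degrees of freedom". No empirical (sandwich) standard error is named, so the standard errors are model-based.

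The PedsQL model is fitted twice, to Cycle 13 and then "once including data from the entire study", which takes in the long-term follow-up visits. The NRS-11 and PII models (SAP 6.11.2.3.1 and 6.11.2.3.2) choose the covariance in the same way and stop earlier. For NRS-11: "This model will be fitted twice, once using only data through Cycle 13, and once through Cycle 24". The tumor-volume model (SAP 6.11.3.6) also borrows the rule and runs "for all scheduled visits up until the first point where there are fewer than 5 participants with valid tumor volume measurements". All four report least-squares means with standard errors, 95% intervals and p-values at each visit.

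**The concern.** Because the first structure to converge is used, the order of the list decides which model is reported. If a two-parameter, equal-variance structure stands ahead of one with a separate variance for each visit, the richer structure is reached only when the simpler one fails. That is the reverse of the stated rule.

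Model-based standard errors depend on the variance assumed at each visit. If the true variance changes over time and a common one is fitted, the intervals and p-values at individual visits are miscalibrated. This could matter in the long fits, where late visits are sparse and the full unstructured matrix is least likely to converge.

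**Working it through.** **1. Does the list follow the rule?** Count covariance parameters for t visits.

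| Listed order | Formula | t = 5 | t = 8 | t = 12 |
|---|---|---|---|---|
| Unstructured | t(t+1)/2 | 15 | 36 | 78 |
| Heterogenous Toeplitz | 2t − 1 | 9 | 15 | 23 |
| Heterogenous Autoregressive | t + 1 | 6 | 9 | 13 |
| Autoregressive | 2 | 2 | 2 | 2 |
| Heterogenous Compound Symmetry | t + 1 | 6 | 9 | 13 |
| Compound Symmetry | 2 | 2 | 2 | 2 |
| Variance Components | 1 | 1 | 1 | 1 |

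The count rises at one step, from Autoregressive to Heterogenous Compound Symmetry, at every t. The rule and the list cannot both be followed.

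**2. Which fits are exposed?** SAP Table 13 gives 5 post-baseline PRO visits to Cycle 13 and 8 to Cycle 24. PedsQL then adds a visit every 4 cycles. Tumor volume has 6 visits to Cycle 24 (SAP Table 12) and also continues. Each cohort has about 50 participants (SAP 2.3), fewer for the age-restricted questionnaires.

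**3. How likely is Autoregressive to be reached?** Unstructured, Heterogenous Toeplitz and Heterogenous Autoregressive must all fail first. This was checked by REML simulation in Python, not SAS. The assumptions were 50 participants, a baseline covariate, monotone dropout, a correlation of 0.85 per 56 days, and an SD rising linearly to 1.5 times its first value (with a constant SD also run at 8 visits).

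- 5 visits (the Cycle 13 fit, 42 left at the end): Unstructured converged in 20 of 20 runs.
- 8 visits, 30 left at the end: Heterogenous Autoregressive converged in 300 of 300 runs, both with a constant SD and with 1.5-fold growth.
- 12 visits falling to 5 participants: Unstructured 0 of 2, Heterogenous Toeplitz 3 of 8, Heterogenous Autoregressive 50 of 50, Heterogenous Compound Symmetry 50 of 50.

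The first two structures are fragile in a long fit, on few runs. The third held throughout.

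**4. What if an equal-variance model is reached?** With complete data, a nominal 95% interval for a visit mean that uses a pooled SD covers

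coverage = 2Φ(1.96 × SD_pooled / SD_visit) − 1.

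Assume the SD rises linearly from 1 to R over 8 visits, and take SD_pooled as the root mean square of the 8 values. For R = 1.5, SD_pooled = 1.2607. At the last visit, 2Φ(1.96 × 1.2607/1.5) − 1 = 2Φ(1.647) − 1 = 0.900. At the first, 2Φ(2.471) − 1 = 0.987.

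| Last-to-first SD ratio R | First visit | Last visit |
|---|---|---|
| 1 | 0.950 | 0.950 |
| 1.25 | 0.973 | 0.923 |
| 1.5 | 0.987 | 0.900 |
| 2 | 0.997 | 0.868 |

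If the SD fell by the same ratios, the two columns would swap.

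The 8-visit simulation, with approximate degrees of freedom in place of Kenward-Roger, agrees. At R = 1.5 (300 runs), last-visit coverage was 0.893 with Autoregressive, 0.963 with Heterogenous Compound Symmetry and 0.963 with Heterogenous Autoregressive. At R = 2 (120 runs) it was 0.883 with Autoregressive and 0.950 with Heterogenous Compound Symmetry. With a constant SD, Autoregressive gave 0.957 at the first visit and 0.960 at the last.

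**The case against.** The list is explicit and can be applied mechanically, so pre-specification is intact whichever word describes the order. It can also be read as grouped by family, with the autoregressive pair before the compound-symmetry pair. More importantly, leaving Unstructured does not mean landing on Autoregressive. Two structures with visit-specific variances come first, and one of them, Heterogenous Autoregressive, has the same number of parameters as Heterogenous Compound Symmetry and never failed in the convergence runs above. In those runs the reorder would have changed no selected model. Nothing decisive rests on these fits either. SAP 5.8 makes Cycle 13 the PRO timepoint, and that has its own 5-visit fit. The tumor-volume model is exploratory. Observed SDs are tabulated by visit, so a changing variance would be visible.

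Most of this stands and limits the size of the point. It does not remove the contradiction between rule and list.

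A reader might infer that very sparse late visits force the fallback. For PedsQL the SAP says only that visits with fewer than 5 participants are not presented, not that they leave the model. With one participant at a visit, the visit mean absorbs the observation and a visit-specific variance is not identified. But this affects Heterogenous Compound Symmetry as much as Heterogenous Autoregressive, so order would not decide the outcome. Small 10-visit REML checks were mixed. One found no degenerate fit under either structure in 25 of 25 runs at each of 1 to 5 participants. Another found both unidentified or degenerate in 20 of 20 with one participant, Heterogenous Autoregressive alone degenerate in 2 of 20 with two, and neither with 3 or 5. Order could therefore matter occasionally, but the documents do not show that it will.

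**Conclusion.** The inconsistency is certain: by parameter count, Autoregressive (2) is listed before Heterogenous Compound Symmetry (t + 1), against the stated rule, and four sets of models inherit the list. The effect is conditional on three structures failing first, which looks uncommon, though SAS may behave differently from the check. If it happens and variance differs by visit, last-visit coverage of about 92%, 90% or 87% corresponds to SD growth of 1.25, 1.5 or 2 times. That growth is an assumption.

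Two stronger readings are tempting and not supported. One is that late-visit PedsQL and tumor-volume results will look too favourable, or that their intervals are wrong. That needs both a fit that lands on an equal-variance structure and an SD that rises over time, and the documents establish neither.

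The other is that unequal visit spacing leads to the equal-variance model. PRO visits are 56 days apart to Cycle 9, then 112, 112, 112 and 90 days to Cycle 24, and autoregressive and Toeplitz structures indexed by visit ignore this. But spacing does not determine which structure converges. In the constant-SD simulation, which used these visit days, it did no visible harm to the intervals. MRI visits are nearly evenly spaced in any case (112 days, with 90 and 106 around Cycle 24).

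The point is minor. The primary response-rate analysis is untouched, and the Cycle 13 PRO fit should usually keep Unstructured.

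**What to change.** In SAP 6.11.2.2, move Heterogenous Compound Symmetry up one place, so that the order is:

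1. Unstructured
2. Heterogenous Toeplitz
3. Heterogenous Autoregressive
4. Heterogenous Compound Symmetry
5. Autoregressive
6. Compound Symmetry
7. Variance Components

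At 8 visits the counts become 36, 15, 9, 9, 2, 2, 1, which never increase (items 3 and 4 tie, as do 5 and 6). NRS-11, PII and tumor volume pick up the change by cross-reference. The cost is one edited sentence and a swap in the program, with no effect on data or sample size.

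The reorder lowers the risk of an equal-variance fit without removing it, since the list still ends in such structures. A switch to a spatial power structure is not needed for this point: in its plain form it also assumes one common variance.
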